
To be assessed at Week 52
 
 
To evaluate long-term efficacy of relugolix 40 mg once daily co-administered with low-dose estradiol and norethindrone acetate for up to 52 weeks, among patients who previously completed a 24-week treatment period in one of the parent studies (MVT-601-3101 or MVT-601-3102), on endometriosis-associated pain.
 
 
To be assessed at Week 104
 
 
To evaluate long-term efficacy of relugolix 40 mg once daily co-administered with low-dose estradiol and norethindrone acetate for up to 104 weeks, among patients who previously completed a 24-week treatment period in one of the parent studies (MVT-601-3101 or MVT-601-3102), on endometriosis-associated pain.
 
	
To be assessed at Week 52
 
 
Proportion of women who respond or maintain response at Week 52/Early Termination, based on their dysmenorrhea Numerical Rating Scale (NRS) scores;
 
Proportion of women who respond or maintain response at Week 52/Early Termination, based on their NMPP NRS scores.
 
 
To be assessed at Week 104
 
 
Proportion of women who respond or maintain response at Week 104/Early Termination, based on their dysmenorrhea NRS scores;
 
Proportion of women who respond or maintain response at Week 104/Early Termination, based on their NMPP NRS scores.
 

Secondary Efficacy	

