### 7.1. Adverse Event Definitions

#### 7.1.1. Adverse Event

**Adverse event:** An adverse event is any unfavorable and unintended sign (including an abnormal laboratory finding), symptom, or disease (new or exacerbated) temporally associated with the use of a medicinal product, whether or not related to the medicinal product.

Events meeting the definition of an adverse event **include:**

- A worsening, excluding minor fluctuations, in the nature, severity, frequency, or duration of a pre-existing condition;
- Development of an intercurrent illness during the study;
- Development of symptoms that may or may not be related to the use of a concomitant medication or investigational product;
- Injury or accidents: If a medical condition is known to have caused the injury or accident, the medical condition and the accident should be reported as 2 separate medical events (eg, for a fall secondary to dizziness, both “dizziness” and “fall” should be recorded separately); and
- An investigational abnormality (eg, laboratory parameter, vital sign, ECG) only if the abnormality is considered clinically significant by the investigator based on at least one of the following criteria:
  - Induces clinical signs or symptoms;
  - Requires active intervention;
  - Requires interruption or discontinuation of study drug.

---

Events that **do not** meet the definition of an adverse event include:

- Medical or surgical procedures (eg, surgery, endoscopy, tooth extraction, transfusion); the condition that leads to the procedure is an adverse event;
- Pre-existing diseases or conditions present or detected before the start of study drug administration that do not worsen;
- Situations where an untoward medical event has not occurred (eg, planned hospitalization for an elective procedure, with elective defined as known or planned at the time of signing of the informed consent);
- Endometriosis-associated pain is not considered an adverse event in this study because it is being quantitatively measured as the primary efficacy endpoint.

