### **7.1.2. Serious Adverse Event**

A serious adverse event is any untoward medical occurrence that, at any dose:

- a. Results in death;
- b. Is life-threatening;

NOTE: The term “life-threatening” in the definition of “serious” refers to an event in which the study participant was at risk of death at the time of the event. It does not refer to an event, which hypothetically might have caused death, if it were more severe. For example, drug-induced hepatitis that resolved without evidence of hepatic failure would not be considered life-threatening even though drug-induced hepatitis can be fatal.

- c. Requires hospitalization or prolongation of existing hospitalization;

NOTE: In general, hospitalization signifies that the patient has been admitted to a hospital, independent of the duration of that hospitalization. Complications that occur during hospitalization are adverse events. If a complication prolongs hospitalization or fulfills any other serious criteria, the event is serious. When in doubt as to whether “hospitalization” occurred or was necessary, the adverse event should be considered serious. Hospitalization for elective treatment of a pre-existing condition that did not worsen from baseline is not considered an adverse event.

- d. Results in persistent or significant disability/incapacity;

NOTE: The term disability means a substantial disruption of a person’s ability to conduct normal life functions. This definition is not intended to include experiences of relatively minor medical significance such as uncomplicated headache, nausea, vomiting, diarrhea, influenza, and accidental trauma (eg, sprained ankle) which may interfere or prevent everyday life functions but do not constitute a substantial disruption.

- 
- e. Is a congenital anomaly/birth defect;
  - f. Important medical events which jeopardize the patient and may require medical or surgical intervention to prevent one of the outcomes listed above. Examples of such events are invasive or malignant cancers, intensive treatment in an emergency room or at home for allergic bronchospasm, blood dyscrasias or convulsions that do not result in hospitalization, or development of drug dependency or drug abuse.

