### **9.4. Efficacy Analyses**

Unless otherwise specified, efficacy analyses will be conducted using the mITT Population.

Efficacy endpoints will be summarized by the original treatment groups assigned in the parent study.

The point estimates and 2-sided 95% confidence intervals (CI) for the primary efficacy endpoints (proportion of responders based on dysmenorrhea NRS scores and use of rescue analgesic

medications, proportion of responders based on NMPP scores and use of rescue analgesic medications) will be calculated.

A responder at a given time point and for a specific type of pain (dysmenorrhea or NMPP) is defined as a patient who had a reduction in that type of pain from Baseline in the parent study greater than or equal to a pre-determined threshold and who did not have an increase in the use of rescue analgesic medications for endometriosis-associated pain compared with the use at Baseline. Patients who had a pain reduction less than the pre-determined threshold or who had an increase in the use of analgesics for endometriosis-associated pain will be considered non-responders. The pain reduction thresholds will be determined for NMPP and dysmenorrhea separately (see the SAP for details) for the parent studies and these same thresholds will be applied to this study.

Baseline values are calculated using the Baseline pain assessment period, which is defined as the period from the date of the first dose of placebo in the parent study Run-In Period through the day prior to the first dose of randomized study drug. Patients' average NRS pain scores and use of rescue analgesic medications for endometriosis-associated pain (dysmenorrhea or NMPP) will be compared between a given visit-specific pain assessment period (eg, Week 28, Week 32, etc.) and the Baseline pain assessment period. The visit-specific pain assessment period is defined as the last 35 calendar days immediately prior to and including the last dose of study drug treatment received prior to the visit date.

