For any pain assessment period (Baseline or visit-specific), the average NRS scores will be calculated for dysmenorrhea and NMPP separately. An average NRS score for dysmenorrhea is calculated as the average NRS score over the days with menses during a given pain assessment period. An average NRS score for NMPP is calculated as the average NRS score over the days without menses during a given pain assessment period. The analgesic use for a given pain assessment period is summarized by total dose count defined as the average daily dose count taken during the given pain assessment period multiplied by 35. Additional details on calculating dose counts and on the precise definition of an increase in analgesic use will be provided in the SAP.

Descriptive statistics will be provided for efficacy endpoints (listed below) similar to those used for the parent studies at Week 52 and Week 104.

- Change from the parent study Baseline in the EHP-30 Pain Domain scores;
- Change from the parent study Baseline to in the mean dysmenorrhea NRS score;
- Proportion of patients who are better or much better on the PGIC for dysmenorrhea;
- Change from the parent study Baseline in the mean NMPP NRS score;
- Proportion of patients who are better or much better on the PGIC for NMPP;
- Change from the parent study Baseline in the mean dyspareunia NRS scores;
- Proportion of patients who are better or much better on the PGIC for dyspareunia;
- Change from the parent study Baseline in the mean dyspareunia functional impairment on the sB&B scale;
- Change from the parent study Baseline in severity scores on the PGA for pain;

- 
- Proportion of responders based on EHP-30 Pain Domain scores;
  - Change from the parent study Baseline in function impairment on the PGA for function;
  - Change from the parent study Baseline in each of the non-pain EHP-30 domains (Control and Powerlessness, Social Support, Emotional Well-Being, and Self-Image);
  - Change from the parent study Baseline pain assessment period in dysmenorrhea-related functional effects (sB&B);
  - Change from the parent study Baseline pain assessment period in NMPP-related functional effects (sB&B).

For binary endpoints, the point estimate and 2-sided 95% CI for the proportion will be provided by parent study treatment group.

For endpoint of proportion of responders based on EHP-30 Pain Domain scores, a responder is defined using the same within-patient score change threshold determined from the parent studies.

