#### **6.5.1.2. Patient eDiary**

All women enrolled in the study will continue to use the patient eDiary dispensed in the parent study (see Appendix 2). Patients will complete daily eDiary entries, including NRS pain scores, menstruation information, analgesic drug use, date and time of study drug administration, and sB&B scale scores until Week 52. After Week 52, eDiary scores will be entered over four eDiary collection cycles on the following schedule: Week 57 to the Week 65 visit, Week 71 to the Week 78 visit, Week 85 to the Week 91 visit, and Week 98 to the Week 104 visit.

The site should review the eDiary data at every visit.

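### The blanket exclusion of endometriosis pain from adverse events rests on a reason that does not cover the whole safety period, and it conflicts with the protocol's own rules on worsening and seriousness

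*Protocol*

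**What the plan says.** In its list of what is not an adverse event, Protocol Section 7.1.1 says: "Endometriosis-associated pain is not considered an adverse event in this study because it is being quantitatively measured as the primary efficacy endpoint". It adds no ceiling on severity, no exception for serious events and no time limit. The same section's list of what does count includes: "A worsening, excluding minor fluctuations, in the nature, severity, frequency, or duration of a pre-existing condition".

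Section 7.1.2 defines a serious adverse event from any untoward medical occurrence that meets a criterion, one of which is "Requires hospitalization or prolongation of existing hospitalization". Its note on hospitalization exempts only elective treatment of a pre-existing condition that is no worse than at baseline.

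On measurement, Section 3 gives the second-year primary endpoint as "Proportion of women who respond or maintain response at Week 104/Early Termination, based on their NMPP NRS scores", with a matching endpoint for dysmenorrhea. Section 9.4 defines the pain window as "the last 35 calendar days immediately prior to and including the last dose of study drug treatment received prior to the visit date", and plans summaries of the other efficacy endpoints "similar to those used for the parent studies at Week 52 and Week 104". Section 6.5.1.2 says: "After Week 52, eDiary scores will be entered over four eDiary collection cycles on the following schedule"; the cycles are Weeks 57 to 65, 71 to 78, 85 to 91 and 98 to 104. Section 4.1, however, describes pain recording through the 80-week period and the Follow-Up of about 30 days, and Table 1-1 marks the daily diary at Follow-Up.

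Under Section 7.2.1, adverse events are collected until the Follow-up visit about 30 days after the last dose, or until certain other therapy or surgery starts, if earlier. Section 9.5 summarizes discontinuations due to adverse events.

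Sections 7 and 9 are available only in the Amendment 2 text. The later version breaks off within Section 6.5.2.6. Its diary schedule is the same, but whether its Sections 7.1.1 or 9.4 changed cannot be seen.

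**The concern.** Keeping the disease symptom out of the adverse event tables is reasonable where an efficacy endpoint already captures it. The protocol gives that as its only reason, so the exclusion is justified only where an endpoint does capture the pain. For much of the second year, and for all of Follow-Up, none does.

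The exclusion also gives sites two instructions for the same event. A woman admitted unexpectedly for worsened pelvic pain has a worsened pre-existing condition and a hospitalization, both reportable. She also has endometriosis-associated pain, which is not an adverse event at all.

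Adverse event incidence is a named safety endpoint at Weeks 52 and 104. If sites resolve the conflict differently, counts of serious adverse events and of discontinuations due to adverse events will depend on local reading. The events at risk of omission, loss of pain control severe enough for admission or for stopping treatment, matter for a long-term treatment.

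**Working it through.** The plan gives no figure of its own here, so the check is a day count followed by a comparison of the texts.

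**Inputs.** The second year runs from Week 52 to Week 104. The diary cycles come from Section 6.5.1.2, the 35-day window from Section 9.4, and the primary time point, Week 104/Early Termination, from Section 3. Visits are taken at their nominal weeks.

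**Day counts**

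- Second year: (104 − 52) × 7 = 364 days.
- Diary on: 8 + 7 + 6 + 6 = 27 weeks = 189 days; 189/364 = 51.9%.
- Diary off: 5 + 6 + 7 + 7 = 25 weeks = 175 days; 175/364 = 48.1%.
- Primary endpoint window at Week 104 only: 35/364 = 9.6%, leaving 329 days (90.4%) outside.
- If Weeks 65, 78, 91 and 104 each have a window: 4 × 35 = 140 days; 140/364 = 38.5%, leaving 224 days (61.5%) outside.
- Follow-Up: the window ends at the last dose, so none of the roughly 30 days falls in an endpoint window.

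The first window figure follows the named endpoints, since Sections 3 and 9.4 name only Weeks 52 and 104. The second is the more generous reading, because Section 9.4 defines the window for each visit.

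Moving all four second-year visits 7 days early or late, with the cycle starts fixed, gives outer bounds for diary coverage of (189 − 28)/364 = 44% and (189 + 28)/364 = 60%.

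**The texts side by side, for an unplanned admission for worsened pelvic pain**

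- Section 7.1.1, worsening rule: an adverse event.
- Section 7.1.1, pain exclusion: not an adverse event.
- Section 7.1.2, definition: an untoward occurrence with hospitalization, so serious.
- Section 7.1.2, exemption: does not apply, because the admission is not elective and the condition did worsen.

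The pain exclusion is the more specific rule and carries a stated reason, so a site could let it prevail. It could equally follow Section 7.1.2 and report.

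For a woman who stops study drug because of pain, the exclusion points one way only: her pain is not an adverse event, so her stopping is not a discontinuation due to one.

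**The case against.** The strongest reply is that the pain is measured and the exclusion is a deliberate exception to a general rule. Much of this stands.

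- A reader might infer that pain goes unmeasured in most of the second year and in Follow-Up. The documents do not support that. The diary is scheduled on about 52% of second-year days and is marked at Follow-Up, with site review. The patient global assessment of pain is taken at every on-treatment visit, although it asks only about pain at that moment and is not scheduled at Follow-Up. The gap is in what feeds an endpoint.
- A reader might infer that severe worsening disappears from every efficacy table. It does not. Changes in mean NRS scores, the pain global assessment and the EHP-30 Pain Domain are secondary endpoints and would reflect it at Weeks 52 and 104. Women who stop early enter the primary endpoint through its Early Termination arm.
- A reader might infer that a hospitalization for pain must go unreported. Section 7.1.2 is worded broadly enough for a site to report it. Omission is one reading of conflicting text.
- Section 5.7 refers uncontrolled pain to the medical monitor, and Section 10.1.6 requires the reason for withdrawal to be recorded. Both help individual oversight, but neither puts the event into an adverse event count.

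A named exception may override a general rule, which weakens the conflict with the worsening rule taken alone. It does not settle the conflict with Section 7.1.2, which has its own narrower exemption.

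**Conclusion.** The point holds in limited form. The stated reason for the exclusion covers 9.6% of second-year days on the named primary endpoint, or 38.5% if every second-year visit has a window, and no Follow-Up days. Sections 7.1.1 and 7.1.2 give opposing instructions for an unplanned hospitalization for worsened pain. As written, such an event can be left out of serious adverse event counts, and a discontinuation because of pain can be left out of adverse event discontinuations. How often this would happen cannot be estimated from the documents.

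It may be tempting to go further and count every worsening from parent-study Baseline as an adverse event. The documents do not make that case. Such a rule would have no threshold, would duplicate the efficacy endpoints, and would alter adverse event tables that start at the first parent-study dose.

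The conclusion assumes nominal visit timing and the four-cycle diary schedule, rather than the continuous recording described in Section 4.1. It also assumes that Sections 7.1.1 and 9.4 are unchanged in the later version.

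**What to change.** Reconcile Section 7.1.1 with Section 7.1.2. State that endometriosis-associated pain is not an adverse event unless it meets a seriousness criterion or leads to discontinuation of study drug, and that this applies through the Follow-up visit. Show these events on a separate line of the adverse event tables, so that incidence can be read with and without them. The separate line matters because the tables pool extension and parent-study data, and the parent studies' own definition is not shown.

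In the same edit, align Section 4.1's description of continuous diary recording with the four cycles in Section 6.5.1.2. If Section 7.1.1 has already been revised in the later version, check that text first.

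This is a change to a reporting definition and leaves patient management as it is. It costs about two sentences and one table line, a few more reports, and a slightly higher reported incidence.

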### **7.1.2. Serious Adverse Event**

A serious adverse event is any untoward medical occurrence that, at any dose:

- a. Results in death;
- b. Is life-threatening;

NOTE: The term “life-threatening” in the definition of “serious” refers to an event in which the study participant was at risk of death at the time of the event. It does not refer to an event, which hypothetically might have caused death, if it were more severe. For example, drug-induced hepatitis that resolved without evidence of hepatic failure would not be considered life-threatening even though drug-induced hepatitis can be fatal.

- c. Requires hospitalization or prolongation of existing hospitalization;

NOTE: In general, hospitalization signifies that the patient has been admitted to a hospital, independent of the duration of that hospitalization. Complications that occur during hospitalization are adverse events. If a complication prolongs hospitalization or fulfills any other serious criteria, the event is serious. When in doubt as to whether “hospitalization” occurred or was necessary, the adverse event should be considered serious. Hospitalization for elective treatment of a pre-existing condition that did not worsen from baseline is not considered an adverse event.

- d. Results in persistent or significant disability/incapacity;

NOTE: The term disability means a substantial disruption of a person’s ability to conduct normal life functions. This definition is not intended to include experiences of relatively minor medical significance such as uncomplicated headache, nausea, vomiting, diarrhea, influenza, and accidental trauma (eg, sprained ankle) which may interfere or prevent everyday life functions but do not constitute a substantial disruption.

- 
- e. Is a congenital anomaly/birth defect;
  - f. Important medical events which jeopardize the patient and may require medical or surgical intervention to prevent one of the outcomes listed above. Examples of such events are invasive or malignant cancers, intensive treatment in an emergency room or at home for allergic bronchospasm, blood dyscrasias or convulsions that do not result in hospitalization, or development of drug dependency or drug abuse.

## 7.2. Adverse Event Reporting

The reporting of serious adverse events by the sponsor (Myovant Sciences GmbH) to regulatory authorities is a requirement and each authority has a timetable for reporting these events based upon established criteria. Likewise, it is the responsibility of the investigator to report serious adverse events to their local Institutional Review Board (IRB) or Independent Ethics Committee (IEC).

Care will be taken not to introduce bias when detecting adverse events and/or serious adverse events. Open-ended and non-leading verbal questioning of the patient is the preferred method to inquire about adverse event occurrence. Appropriate questions include:

- “How are you feeling?”
- “Have you had any (other) medical problems since your last visit/contact?”
- “Have you taken any new medicines, other than those provided in this study, since your last visit/contact?”

The patient’s eDiary entries, including bleeding and answers to the other patient-reported outcome measures, will not be used as a primary means to collect adverse events, however they should be reviewed by the study site personnel and the study monitors. Should the investigator or site staff become aware of a potential adverse event through the information collected with these instruments, proper follow-up with the patient for medical evaluation should be undertaken. Through this follow-up, if it is determined that an adverse event not previously reported has been identified, normal reporting requirements should be applied.

All patients who experience an adverse event will be evaluated at appropriate time intervals until the event resolves or has stabilized or become chronic. At the conclusion of the study, the investigator and medical monitor will assess unresolved adverse events and determine if additional follow-up is warranted.

All adverse events, whether or not related to the study drug treatment, must be fully and completely documented on the adverse event case report form and in the patient’s source documents. In addition, any adverse event resulting in permanent treatment discontinuation must be recorded on the appropriate case report form as well as documented in the patient’s source documents. Adverse event terms should include a diagnosis, as available, in preference to listing the individual signs and symptoms. If the diagnosis is not known, the investigator should record each sign and symptom as an individual adverse event.

Overdose and pregnancy in the patient will be reported as described in Section 7.7 and Section 7.8, respectively.

